1.0 TRIAL SUMMARY

Abbreviated Title	MK-3475 in larynx cancer
Trial Phase	Phase I/II
Clinical Indication	Locally advanced stage III and IV larynx cancer
Trial Type	Open label single arm study
Type of control	None
Route of administration	IV
Trial Blinding	None
Treatment Groups	Single Arm Combination study
Number of trial subjects	47
Estimated enrollment period	18 months
Estimated duration of trial	24 months
Duration of Participation	24 months

2.0 TRIAL DESIGN

2.1 Trial Design

This study is an open label, single arm study which will enroll patients with locally advanced squamous cell carcinomas of the larynx. Positive tumor PDL1 expression by IHC will not be required for enrollment.

All patients will receive Pembrolizumab and cisplatin in combination with radiation. Pembrolizumab 200 mg flat dose given Q21 days will begin 3 weeks prior to initiation of chemoradiation and continued through the 21-day cycle until completion of chemoradiation. Cisplatin will be given 100 mg/m² every 21 days during radiation as per standard of care.

Pembrolizumab has well defined toxicities as single agent and has non-overlapping mechanisms of action with cisplatin and radiation. The safety of these agents used in combination has not been previously described, therefore the study will begin with a safety run-in phase 1 followed by the phase II design. See statistical section for details.

2.1.1 Phase I run in

Both drugs are FDA approved for other disease indications, with safety and tolerability well described at the approved doses. Therefore the limited phase I portion of this study aims to assess the safety and tolerability of this drug combination at their established doses along with concurrent radiation. There will be no dose escalation cohorts within this phase I run in group.

The first six patients will constitute the phase I portion of this study. These initial 6 patients will be assessed for dose limiting toxicities (DLTs, defined in Section 2.1.1.1)

from the start of study treatment until the start of cycle #2 concurrent cisplatin/radiation and pembrolizumab. After these first 6 patients initiate cycle #1, enrollment to the study will be temporarily halted, and a formal DLT evaluation of all 6 patients will be conducted.

If ≤ 2 of these six patients experience DLTs after completion of cycle #1 concurrent cisplatin/radiation and Pembrolizumab, then the study will proceed to the phase II portion, using Pembrolizumab 200mg IV Q21 days and cisplatin 100mg IV each 21 day cycle.

If > 2 of these first 6 patients experience a DLT upon completion of cycle #1, the protocol will be amended to investigate use of pembrolizumab 200 mg IV Q 21 days subsequent to completion of chemoradiation. (3-6 weeks after last dose of radiation) (upon Merck approval)

Only upon completion of the DLT evaluation for these first 6 patients and the determination of appropriate Phase II dose, will enrollment reopen for the phase II expansion.

If toxicity results are unclear, we will allow 6 additional patients into Phase I portion (6 + 6). The second cohort will be assessed based on above definitions for DLTs. Unclear toxicity can include (but not limited to) adverse effects that are considered secondary to cisplatin or radiation and per protocol are not considered DLT (see section 2.1.1.1 for definition of DLT) , however, the investigator strongly feels they could be related to study drug or exacerbated by concurrent use of study drug and chemoradiation. This investigator initiated study will be under the oversight of the University of Cincinnati IRB and Data and Safety Monitoring committee.

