8.2 Statistical Analysis Plan

Safety run-in phase: Although PD-1 inhibition is not expected to increase the toxicity of chemoradiation therapy, clinical trials of pembrolizumab combined with cisplatin and radiation for locally advanced head and neck carcinoma have not been conducted. In order to protect against unexpected problems a run-in safety analysis will be performed prior to completing the rest of the first stage of study. This safety analysis will occur after 6 analyzable patients are entered into study. Pembrolizumab will be administered initially at the recommended phase II dose of 200 mg q 3 weeks. If more than 2 dose-limiting toxicities (DLTs) in the cohort of 6 patients then pembrolizumab will be given subsequent to completion of chemoradiation. In the event of 0-2 DLT events, the study will proceed as planned. A DLT will be defined as a \geq grade 3 (CTCAE, v.4) adverse event that is definitely, probably, or possibly related to study drug, excluding grade 3 tumor flare and toxicities that are strongly associated with concurrent radiation and cisplatin (for example rash, mucositis, radiation dermatitis).

LFS will be estimated using the Kaplan-Meier method. The point estimate and standard error will be obtained from the Kaplan-Meier curve and a 95% confidence interval will be calculated to estimate 18-month LFS. A z-test will be used to test the primary hypothesis of improvement in 18- month LFS from 70% to 85%.

One-year LFS, Progression-free survival, overall survival, event-free survival, and patterns of failure will be estimated using the Kaplan-Meier method. Complete response at 3 months will be estimated with an exact 95% confidence interval. For correlative studies, prognostic factors for complete response will be identified using logistic regression analysis. Prognostic factors for outcomes will be identified using Cox proportional hazards analysis.

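### The run-in has no pre-specified trigger at the third patient with a DLT, although three such patients already settle the more-than-2-of-6 rule

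*Combined protocol and SAP*

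**What the plan says.** Section 2.1.1 defines the cohort: "The first six patients will constitute the phase I portion of this study". Each patient is assessed for DLTs "from the start of study treatment until the start of cycle #2 concurrent cisplatin/radiation and pembrolizumab". The halt comes late in the sequence: "After these first 6 patients initiate cycle #1, enrollment to the study will be temporarily halted". One evaluation follows: "a formal DLT evaluation of all 6 patients will be conducted". The failure rule is "If > 2 of these first 6 patients experience a DLT upon completion of cycle #1, the protocol will be amended".

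Section 8.2 has the same structure: "This safety analysis will occur after 6 analyzable patients are entered into study". It refers only to entry of six analyzable patients; completion of cycle 1 as the point at which the rule is read comes from sections 2.1.1 and 2.1.2. Section 8.2 also words the rule differently: "If more than 2 dose-limiting toxicities (DLTs) in the cohort of 6 patients then pembrolizumab will be given subsequent to completion of chemoradiation". That counts events, whereas section 2.1.1 counts patients.

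Other provisions bear on safety in the run-in. Section 5.9 deals with the individual patient who has a DLT. Section 5.10 allows the trial to end when adverse reactions indicate a potential hazard to health. Section 10.5 names a DSMB, and section 10.6 has the research team review adverse events weekly. None of them refers to the number of run-in patients with a DLT.

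**The concern.** The rule is a count with a fixed ceiling. Once three run-in patients have a DLT, later patients cannot bring the result back to 2 or fewer, and section 5.9 replaces only patients who had no DLT. A run-in patient who then starts treatment adds nothing to the go/no-go decision, yet receives a schedule that has failed the protocol's own criterion. Section 2.1 says that the safety of the combination had not been described before, which is why the run-in exists, and the patients are previously untreated and treated with curative intent.

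Read literally, sections 2.1.1 and 8.2 let this happen to patients 4, 5 and 6. The question is how often it would happen.

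**Working it through.** The documents state no operating characteristics for the run-in, so there is no figure to reproduce.

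**Inputs from the documents**
- Cohort of 6; failure at 3 or more patients with a DLT (section 2.1.1).
- Accrual: 47 patients in 18 months (section 8.1), so 47/18 = 2.6 per month, or one patient about every 11.7 days.
- DLT window: first pembrolizumab dose to the start of cycle 2. With a 3-week lead-in and a 3-week cycle, this is 21 + 21 = 42 days.

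**Assumptions (not in the documents)**
- True DLT rate p between 20% and 60%.
- DLT onset uniform over the 42 days, and each DLT recognized at onset.
- Random (exponential) gaps between patients.

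**Step 1: probability that the run-in fails.** P(fail) = sum over k = 3 to 6 of C(6,k) p^k (1−p)^(6−k). At p = 20% this is 1 − (0.262 + 0.393 + 0.246) = 9.9%. The other values are in the table.

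**Step 2: upper bound.** If each patient were observed in full before the next one started, the rule would be settled before patient 6 whenever the first five include 3 or more with a DLT: 5.8%, 20.5%, 31.7% and 68.3% of run-ins at p = 20%, 33%, 40% and 60%. Staggered entry at the planned pace makes the real figure smaller.

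**Step 3: planned accrual.** In simulated run-ins I counted those with at least one of the six patients first dosed after the third DLT. The share of all run-ins is P(fail) times the share among failing run-ins.

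| DLT rate | P(fail) | Share of failing run-ins | Share of all run-ins |
|---|---|---|---|
| 20% | 9.9% | 20% | 0.099 × 0.20 = 2% |
| 33% | 31.3% | 24% | 0.313 × 0.24 = 8% |
| 40% | 45.6% | 27% | 0.456 × 0.27 = 12% |
| 60% | 82.1% | 38% | 0.821 × 0.38 = 31% |

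The mean number of patients first dosed after the third DLT is 0.3 to 0.6 per failing run-in. The maximum is 6 − 3 = 3.

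**Step 4: sensitivity, as a share of failing run-ins over p = 20% to 60%**
- Evenly spaced entry and a 43-day window: 22% to 46%.
- DLTs only in the concurrent phase (days 21 to 42): 11% to 22%.
- Every DLT takes a full 28 days to classify: 4% to 9%.

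**Step 5: effect of stopping at the third patient.** Three patients with a DLT is already more than 2 of 6. Acting at that point leaves P(fail) and P(pass) unchanged at every p.

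**The case against.** A reader might infer that nobody would act on a third DLT. The documents do not support that. Adverse events are reviewed weekly, serious events reach the sponsor within 24 hours, a DSMB monitors the study, and section 5.10 allows the trial to be ended. What is missing is a trigger tied to the count, not oversight.

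The size is also open to challenge. Section 8.2 does not expect added toxicity, section 2.1.1.1 takes many chemoradiation effects out of the DLT count, and section 4.2.2 reports no DLTs in single-agent dose escalation. DLT rates of 40% to 60% are therefore assumptions, and shares among failing run-ins look larger than shares of all run-ins. Section 2.1.1.1 also excludes most grade 3 immune-related events that resolve to grade 1 or less within 28 days, so some events cannot be called DLTs at onset. Section 2.1.1 allows six more patients when toxicity is unclear, in terms that it leaves open. These points stand. They are why the table starts at 20% and reports all run-ins, and why the 28-day bound is shown. They reduce the size but do not supply the missing trigger.

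It is also tempting to count everyone who has not begun concurrent chemoradiation at the third DLT. That is not the gap described here. Most of those patients have already had a first dose, closing enrollment does not help them, cisplatin with radiation is their standard treatment in any case, and how they continue is a clinical matter.

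**Conclusion.** The point holds as a missing pre-specified trigger. Followed as written, sections 2.1.1 and 8.2 allow a run-in patient to be first dosed after the protocol's own failure criterion has been met. Under uniform onset and planned accrual this occurs in about 2% of all run-ins at a 20% DLT rate, rising to 31% at 60%. The figures are lower if DLTs arise only in the concurrent phase, and lower again if classification is slow. No more than three patients are exposed, and on average fewer than one per failing run-in at the planned accrual. All of these figures rest on an assumed DLT rate and onset pattern.

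The go/no-go decision and the primary analysis are unaffected. This is an inexpensive safety improvement, not an error that undermines the design.

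**What to change.** Add to sections 2.1.1 and 8.2: *Once a third patient has a confirmed DLT under section 2.1.1.1, the >2 of 6 criterion is met; no further patient is enrolled or given a first dose, and the formal DLT evaluation is convened at once.*

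Add that new first doses pause while a potential third DLT is being classified. Count patients with a DLT in both sections, so that section 8.2 agrees with section 2.1.1. Leave the handling of patients already on treatment to the sponsor and the monitoring committee.

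The cost is a short amendment and a possible delay of up to 28 days while an immune-related event is classified. The threshold, cohort size and pass/fail probabilities stay as they are, and the existing weekly review is enough to keep the count.

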2.1.1.1 Definition of Dose-Limiting Toxicities

All toxicities will be graded using National Cancer Institute (NCI) CTCAE Version 4.0 (see Appendix).

Dose limiting toxicity (DLT) is defined as the appearance of side effects during treatment that are severe enough to prevent continuation of planned treatment. Dose limiting toxicity is defined as grade 3 or 4 non-hematologic toxicities that is definitely, probably, or possibly related to study drug, excluding alopecia, nausea or vomiting, grade 3 tumor flare, rash, mucositis, radiation dermatitis, need for feeding tube, and grade 3 immune-related events that resolve to grade 1 or less within 28 days. However, Grade ≥ 3 immune-mediated adverse events that include pneumonitis, renal failure nephritis, and elevation of AST, ALT, or bilirubin (with an exception for patients with liver metastases with baseline Grade 2 AST or ALT) should result in discontinuation of pembrolizumab and will be considered DLT (please see Table 3 for details on dose modification) .

In addition, adverse effects that are considered secondary to cisplatin or radiation are not considered DLT (see sections 5.2.1.3 and 5.2.2.7) unless they develop after first dose of pembrolizumab and prior to initiation of cisplatin and radiation. Cisplatin or radiation adverse effects include (but are not limited to):

- Grade 3 or 4 renal impairment (with the exception of renal failure or nephritis determined to be immune-related, which will be considered a DLT).
- Grade 2-4 neurotoxicity including ototoxicity (with the exception of myasthenia gravis and Guillain-Barre syndrome, which will be considered a DLT).
- Grade 3 or 4 mucositis
- Grade 3 or 4 myelosuppression

Although the above should result in dose modifications or delays as stated in section 5.2.1.3, they will NOT be considered DLTs for pembrolizumab on this study, and will NOT interfere with expansion to phase II portion of study.

If a patient is taken off study due to the above and has not yet reached evaluation for toxicity attributed to pembrolizumab, that subject will be replaced with another patient on study.

Non hematologic toxicities that will be attributed to pembrolizumab include:

- Grade 3-4 Pneumonitis
- Grade 3-4 diarrhea/colitis
- Grade 3-4 hyperglycemia
- Grade 3-4 hypophysitis
- Grade 3-4 thyroid dysfunction (hypothyroid or hyperthyroid)
- Grade 3-4 hepatic failure (elevation of AST, ALT, Bilirubin)
- Grade 5 toxicity

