2.1.2 Phase II expansion

After the first 6 patients have been assessed for DLTs upon completion of cycle 1 of treatment, and the appropriate Cisplatin dose and Pembrolizumab dosing determined

for phase II expansion, an additional 41 patients with locally advanced larynx squamous cell carcinoma will be enrolled in this phase I/II study. The entire cohort will be used to assess the safety and efficacy outcomes of interest. Safety stopping rules will be applied in the event of excessive toxicity leading to inability of patients to receive at least 2 doses of cisplatin and complete radiation therapy. If radiation treatment breaks are required, greater than a 10 day radiation treatment break in 6 or more patients will also initiate early stop for safety evaluation.

Patients will be evaluated 14 weeks after completion of radiation (14 ± 2 week after completion of radiation) with radiographic imaging to assess response to treatment. All imaging will be assessed using Response Evaluation Criteria in Solid Tumors (RECIST) 1.1 Adverse events will be monitored throughout the trial and graded in severity according to the guidelines outlined in the NCI Common Terminology Criteria for Adverse Events (CTCAE) version 4.0.

After the end of treatment, each patient will be followed for a minimum of 30 days for adverse event monitoring (serious adverse events will be collected for up to 90 days after the end of treatment). Subjects will have post-treatment follow-up for laryngectomy event and survival status for two years.

Participation in this trial will be dependent upon supplying tumor tissue from a formalin-fixed specimen. Newly obtained formalin-fixed specimens are strongly encouraged 14-20 days after first dose of Pembrolizumab prior to initiation of cisplatin and radiation unless clinically deemed unsafe by the treating physician. The specimen will be evaluated for expression status of PD-L1.

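### The run-in rule scores a pembrolizumab-related death as one DLT, so two such deaths in six patients still meet the written condition to expand, and no numeric rule counts deaths afterwards

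*Combined protocol and SAP*

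**What the plan says.** Section 2.1.1 sets the run-in: "The first six patients will constitute the phase I portion of this study". The go condition is that if at most two of them "experience DLTs after completion of cycle #1 concurrent cisplatin/radiation and Pembrolizumab, then the study will proceed to the phase II portion". The other branch reads "If > 2 of these first 6 patients experience a DLT upon completion of cycle #1, the protocol will be amended". Section 8.2 gives the same limit in different units: "In the event of 0-2 DLT events, the study will proceed as planned".

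Death appears in the DLT section (2.1.1.1) only as the last item, "Grade 5 toxicity", in a list of non-hematologic toxicities that are attributed to pembrolizumab. The main definition in that section speaks of grade 3 or 4. Section 8.2 uses grade 3 or higher. Section 2.1.1.1 also takes effects considered secondary to cisplatin or radiation out of the DLT count, unless they arise between the first pembrolizumab dose and the start of chemoradiation. Of the listed examples, which stop at grade 4, it says "they will NOT be considered DLTs for pembrolizumab on this study, and will NOT interfere with expansion to phase II portion of study".

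The DLT window closes at the start of concurrent cycle 2. If toxicity is unclear, section 2.1.1 allows six further run-in patients. For the 41 expansion patients, section 2.1.2 has a rule tied to delivery of cisplatin and of the full radiation course: "Safety stopping rules will be applied in the event of excessive toxicity leading to inability of patients to receive at least 2 doses". It adds a safety stop if radiation breaks of more than 10 days occur in six or more patients. Section 5.10, item 3, allows early termination for the incidence or severity of adverse drug reactions. Sections 2.1.1, 2.1.2.1 and 10.5 place the trial under an IRB and a data and safety monitoring body.

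**The concern.** Section 4.2.1 says the combination of pembrolizumab and chemoradiation has not been examined in humans, and section 5.1.1 enrols patients who are candidates for curative treatment. In that setting one would expect a treatment-related death to prompt review in its own right. Here the only explicit numeric rule treats it as equal to a non-fatal grade 3 DLT. Taken literally, it directs the trial to open expansion after one or even two drug-related deaths in six patients.

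Once expansion is open, the written numeric limits no longer look at drug toxicity or death. At stake is whether a fatal signal stops enrolment because the plan says so, or only because someone chooses to intervene against a rule that says proceed.

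**Working it through.** **No plan figure to reproduce.** The documents state no error rate or operating characteristic for the run-in rule. The inputs are six run-in patients and the 0-2 limit (2.1.1, 8.2), 41 expansion patients (2.1.2) and 47 in total (8.1): 6 + 41 = 47, so 41/47 = 87% are treated after the run-in decision.

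**Step 1: score a death under each rule.**

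| Place | What it acts on | Number given | Does a death register? |
|---|---|---|---|
| 2.1.1 | run-in patients with a DLT | proceed on 2 or fewer of 6 | as one patient |
| 8.2 | DLT events in the six | proceed on 0-2 | as one event |
| 2.1.1, further six | unclear toxicity | none for the second cohort or for 12 patients | only if judged unclear |
| 2.1.2, delivery | toxicity preventing two cisplatin doses and full radiation | none | indirectly, if it prevents delivery |
| 2.1.2, breaks | radiation break over 10 days | 6 or more patients | not as a death |
| 5.10, item 3 | adverse drug reactions | none | by judgement |
| 10.5 | monitoring board | none | by judgement |

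Two pembrolizumab-related deaths and no DLT in another patient give 2 of 6, which is within the limit in section 2.1.1. Under the event count in section 8.2 the result is the same if each death is that patient's only DLT event. If a patient had separate earlier DLT events, the event count could exceed 2 while the patient count did not.

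**Step 2: what 2 of 6 is compatible with.** The observed rate is 2/6 = 33%. The exact (Clopper-Pearson) 95% limits are the 2.5% quantile of Beta(2, 5) = 0.043 and the 97.5% quantile of Beta(3, 4) = 0.777.

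**Step 3: how often this could arise.** The documents give no death rate, so q below is an assumption. With deaths as the only DLTs, P(k deaths) = C(6, k) q^k (1 - q)^(6 - k). For q = 0.10:

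- P(1) = 6 x 0.1 x 0.9^5 = 0.354
- P(2) = 15 x 0.01 x 0.9^4 = 0.098
- Sum = 0.453

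| Assumed q | 1 or 2 deaths: rule says proceed | 3 or more: rule stops | 1 or more: death-triggered review would pause |
|---|---|---|---|
| 5% | 0.263 | 0.002 | 0.265 |
| 10% | 0.453 | 0.016 | 0.469 |
| 20% | 0.639 | 0.099 | 0.738 |

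Other DLTs lower the middle-case figure. Suppose q = 10% and, in addition, 20% of patients have a non-fatal DLT (also assumed):

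- P(2 or fewer DLT patients at a total rate of 30%) = 0.744
- P(no deaths and 2 or fewer non-fatal DLTs) = 0.7^6 + 6 x 0.2 x 0.7^5 + 15 x 0.2^2 x 0.7^4 = 0.118 + 0.202 + 0.144 = 0.463
- P(at least one death and proceed) = 0.744 - 0.463 = 0.281

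**Step 4: what the count can see.** From concurrent day 1 to the start of cycle 2 is three weeks, so about 3 x 5 = 15 of 35 fractions (43%). By then 1 of at most 3 cisplatin doses and 2 of at most 4 pembrolizumab doses are due (Table 2, section 6.1). Section 5.2.1.2 notes that pembrolizumab events may appear months after the last dose. A death after the window enters no numeric count.

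**Step 5: a death blamed on chemoradiation.** The grade 5 item in section 2.1.1.1 carries no qualifier, which would make such a death one DLT. The exclusion of effects secondary to cisplatin or radiation would make it none. The section does not settle which governs.

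**The case against.** The strongest reply is that the trial is not unguarded. Enrolment halts after the first six for a formal DLT evaluation. Serious adverse events go to the sponsor within 24 hours (7.2.3.1), study staff review adverse events weekly (10.6), and a monitoring board is named. The delivery rule in section 2.1.2 covers toxicity from any agent, so a death during chemoradiation, or pembrolizumab toxicity that ends it, falls within it. Section 5.10, item 3, permits termination. No competent board would wave through two related deaths.

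All of this stands, and it limits the point to the absence of a numeric or death-specific trigger. A reader might infer that nothing watches pembrolizumab toxicity after the run-in; the documents do not support that. But every safeguard listed either carries no number or depends on discretion, while the one explicit count says proceed.

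The optional second cohort also deserves mention. Its trigger is open-ended and can include toxicity blamed on chemoradiation that the investigator suspects is drug-related. It is discretionary, has no threshold of its own, and would not be triggered by deaths that are clearly drug-related.

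A reader might also infer that a death attributed to cisplatin or radiation scores zero. The sentence saying such effects do not count refers to examples that stop at grade 4, and the grade 5 item is unqualified, so this is an ambiguity and not an established score. Nor does the trial's safety conclusion rest on six patients seen through 43% of radiation: section 2.1.2 uses the entire cohort for safety, with adverse events collected to 30 days and serious events to 90. Only the formal DLT decision rests on the six.

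**Conclusion.** The point holds as a literal reading of sections 2.1.1, 2.1.1.1 and 8.2: two pembrolizumab-related deaths in six patients, with no DLT in another patient, satisfy the written condition to expand. Afterwards 41 of 47 patients (87%) are treated without a numeric limit on pembrolizumab toxicity or death.

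The probabilities are illustrations. The 26%, 45% and 64% chances of one or two deaths in six rest on assumed related-death rates of 5%, 10% and 20% and on no other DLTs occurring. The 45% falls to 28% if a 20% non-fatal DLT rate is added. The reading of the rule depends on none of these rates.

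The 0-2 limit for DLTs is not challenged here. What is missing is separate handling of death, and that should be corrected because the remedy is specific and cheap. Continued DLT counting in the expansion would be a reasonable addition but is optional.

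**What to change.** In sections 2.1.1, 2.1.2 and 8.2, state that any death on treatment or within 30 days after it that is not clearly due to the cancer, whichever treatment component it is attributed to, pauses accrual until the data and safety monitoring board has reviewed it. State also that the 0-2 DLT rule does not by itself open expansion after such a death. Because the trigger ignores attribution, it works however the ambiguity in section 2.1.1.1 is settled.

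Reconcile three things: grade 3 or 4 with a separate grade 5 item (2.1.1.1) against grade 3 or higher (8.2); patients with DLTs (2.1.1) against DLT events (8.2); and the unqualified grade 5 item against the exclusion of chemoradiation effects (2.1.1.1).

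If the sponsor and board also want to count DLTs during expansion, they should set the boundaries themselves, using one defined DLT window throughout and stating the operating characteristics.

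The cost is wording. Non-cancer deaths are already reported within 24 hours (7.2.3.1), so no new data are needed. The downside is an occasional pause for a death that proves unrelated. With an assumed 2% of patients having a qualifying death, 47 x 0.02 = 0.9 reviews would be expected over the trial, and with 5%, 47 x 0.05 = 2.4. At the planned 47 patients in 18 months (8.1), each month of pause delays about 47/18 = 2.6 enrolments.
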